5 BASIC STUDY DESIGN

This is a multicenter clinical trial of a cross section of HIV+ patients with and without diastolic dysfunction. Sites currently participating in the Heart Failure Clinical Research Network (HFN) will collaborate with their HIV clinics to identify eligible patients. Approximately 200 HAART-treated virally suppressed HIV+ subjects (100 HIV+/DD+ & 100 HIV+/DD-) will be enrolled. Data will be managed by the HFN Coordinating Center (CC) at Duke University. This study will evaluate biomarkers, phenomapping, metabolomics, cMRI, echocardiography to determine characteristics unique to this patient population. This patient population will then be compared to the MESA (Multi-Ethnic Study of Atherosclerosis) population providing subjects who are HIV-/DD+ (see section 7.0).

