13.2 Power Calculations and Statistical Analysis for Biomarkers

The primary statistical comparison for Aim 1a is the between group (the HIV+/DD+ and HIV+/DD- cohorts) difference in log-transformed IL-6 biomarker levels. Log-transformed IL-6 (log pg/ml) is expected to have a standard deviation of approximately 0.75.⁵² Sample sizes of 100 subjects in each group will provide 80% and 90% power to detect differences of 0.30 and 0.35 (log pg/ml), respectively. These sample size calculations were based on a two-sample t-test with a two-sided type I error of 0.05. Additionally these calculations suggest that any comparison of (properly transformed) continuous variables between the HIV+/DD- and HIV+/DD+ cohorts will have 80% and 90% power to detect differences of 0.40 and 0.46 standard deviations, respectively. Comparisons between the HIV+/DD+ or HIV+/DD- cohorts and the HIV-/DD+ cohort will have greater power due to the larger number of subjects in the HIV-/DD+ cohort. Statistical summaries will use median (25th, 75th percentiles) and mean (standard deviation) for continuous measures and frequencies (percentages) for categorical variables. Because many biomarkers are expected to be right-skewed, we will log-transform each marker or use another appropriate transformation to normalize its distribution. Unadjusted comparisons between groups will be based on t-tests after the appropriate transformations for continuous measures and chi-square tests for categorical measures. For Aim 1a, propensity scores will be the primary tool used to obtain balanced comparisons between cohorts. The propensity score is defined as the probability of having group membership (e.g. HIV+/DD+) conditional on observed covariates and is a commonly used balancing score used in observational studies.⁵³ Three different methods of propensity score adjustment will be applied. The primary analysis method will be based on inverse probability weightings. Secondary approaches will be based on full propensity score matching and doubly-robust estimation.^{54, 55} Distributional overlap and covariate balance will be assessed using the recently developed best practices for propensity score analyses.⁵⁶ The primary adjusted analysis of IL-6 levels between cohorts will be conducted at the two-sided 0.05 level.

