13.6 Integrated Molecular Statistical Analysis

Analytic methods will be used for integration of the multi-dimensional data. Principle components analysis (PCA) with varimax rotation and use of the Kaiser criterion for identification of PCA factors will be tested for discrimination. Models will be further tested with random forests and penalized regression,⁶⁷ either with or without dimension reduction.⁶⁸ To control for flexibility, we will test accuracy of prediction with cross-validation. Although high-throughput -omic technologies are used to predict outcomes, they present challenges related to high-dimensional data spaces created where modest number of samples are often defined by

thousands of measurements. We will utilize Bayesian Factor Regression Models^{69,70} to reduce the effective dimension of the data prior to model building. We will utilize a two-step factor regression approach to building predictive models. First, factor models will be used to aggregate subsets of metabolomics or proteomics data into single meta-genes based on high levels of co-expression.⁷¹ Second, the factors will be used collectively as independent variables to build predictive model, either penalized regression or random forests. Model accuracy for discrimination of DD will be assessed by area under the receiver operating characteristic curves. We will also utilize pathway-based models, assessing for over-representation of the most significant predictors in pathways using Ingenuity Software for Pathway Analysis and biochemical pathway analysis using UniPathway annotation (www.grenoble.prabi.fr/obiwarehouse/unipathway).

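### Section 13.6 relies on plain cross-validation to control flexibility but has no rule for choosing among pipelines; if the best AUC is reported, it will be optimistic

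*Combined protocol and SAP*

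**What the plan says.** Section 5 gives the data available: "Approximately 200 HAART-treated virally suppressed HIV+ subjects (100 HIV+/DD+ & 100 HIV+/DD-) will be enrolled". Section 13.6 then lists these ways of discriminating DD:

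- principal component factors, rotated by varimax and retained by the Kaiser criterion;
- two model types, on reduced or unreduced data: "Models will be further tested with random forests and penalized regression";
- Bayesian factor regression, used to "reduce the effective dimension of the data prior to model building", with the factors then entering one or other of the same two model types.

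The safeguard is one sentence: "To control for flexibility, we will test accuracy of prediction with cross-validation". The measure is given separately: "Model accuracy for discrimination of DD will be assessed by area under the receiver operating characteristic curves".

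The section gives no number of folds, nesting, hold-out set, primary pipeline, selection rule or reporting rule. It does not say whether dimension reduction is repeated within each fold. Section 13.1 promises a statistical analysis plan before the data are analysed, but the document in hand adds nothing on this point.

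Other sections are firmer. Sections 13.2, 13.4 and 13.7 each name inverse probability weighting as primary and the other two propensity methods as secondary. Section 13.5 controls the false discovery rate.

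**The concern.** The protocol offers cross-validation as the remedy for flexibility. Cross-validation deals with one kind: a single pipeline fitting its own training data too closely. It does not deal with trying several pipelines on the same subjects and keeping the one that scored best. The highest of several noisy estimates tends to lie above the true value of the model it came from.

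At stake is how well the molecular profile is said to separate DD+ from DD- in HIV. Nothing described would reveal an inflated figure. In sections 5 and 7, MESA supplies HIV-/DD+ subjects only, so it cannot test DD+ against DD-. The repeat assays in section 13.5 use the same samples and check the assay, not the model.

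**Working it through.** **1. The plan's own figure.** Section 13.6 states no AUC, precision or sample size. The only sizing figure is in section 13.2: "Sample sizes of 100 subjects in each group will provide 80% and 90% power to detect differences of 0.30 and 0.35 (log pg/ml), respectively", with standard deviation 0.75. Normal approximation: power = Φ(δ / (SD·√(2/n)) − 1.96), with SD·√(2/n) = 0.75 × √0.02 = 0.1061.

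- δ = 0.30: Φ(2.828 − 1.96) = 80.7%.
- δ = 0.35: Φ(3.300 − 1.96) = 91.0%.

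The figure reproduces. It concerns a comparison of means and does not bear on the AUC.

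**2. Precision of one AUC, 100 against 100.** Hanley–McNeil: SE² = [A(1−A) + 99(q₁−A²) + 99(q₂−A²)] / 10,000, with q₁ = A/(2−A) and q₂ = 2A²/(1+A). At A = 0.50, q₁ = q₂ = 1/3, so SE² = (0.25 + 16.5)/10,000 and SE = 0.041. At A = 0.65 it is 0.039, and at 0.75 it is 0.034.

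**3. Optimism from reporting the best of K.** For K equally good pipelines whose AUC estimates have correlation ρ, expected optimism = SE·√(1−ρ)·E[maximum of K standard normals]. The documents give neither K nor ρ, so both are assumptions. The list in section 13.6 suggests K of 5 to 7. I take 3 to 14, where 14 is seven pipelines run separately on proteins and on metabolites. At a true AUC of 0.50:

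| K | ρ = 0 | ρ = 0.5 | ρ = 0.9 |
|---|---|---|---|
| 3 | 0.035 | 0.024 | 0.011 |
| 5 | 0.048 | 0.034 | 0.015 |
| 7 | 0.055 | 0.039 | 0.018 |
| 14 | 0.070 | 0.049 | 0.022 |

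At a true AUC of 0.75 and K = 5 the values are 0.040, 0.028 and 0.013.

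**4. Simulation against the truth.** Assumptions: 100 against 100; 1,000 correlated analytes; six surrogate pipelines (ridge, two screened ridge models, two principal component models, bagged stumps in place of a forest); 10-fold cross-validation. Signal was a shift in 20 analytes of 0, 0.2 or 0.4 residual standard deviations, with 100, 100 and 120 data sets. The true AUC of the chosen pipeline was measured on 2,000 new subjects.

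| Signal | Best of six, CV AUC | True AUC of that pipeline | Bias (Monte Carlo SE) | Nested 5×5 CV |
|---|---|---|---|---|
| None | 0.549 | 0.500 | +0.049 (0.005) | 0.492 |
| Weak | 0.583 | 0.522 | +0.061 (0.006) | 0.526 |
| Stronger | 0.709 | 0.694 | +0.015 (0.005) | 0.650 |

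Without selection, the average bias over the six pipelines lay between −0.008 and +0.004, so the bias comes from choosing. With weak signal it exceeds the true departure from 0.5 (0.061 against 0.022). With stronger signal two pipelines clearly led, which left less to choose between.

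**5. A second null simulation.** This used ridge or random forest, each with no reduction, 5 components or 20 components, in 189 data sets. Single pipelines averaged 0.491 to 0.504. The best of six averaged 0.551, with a 95th percentile of 0.622. It exceeded 0.55 in 52% of data sets, against 19% for a single fixed pipeline.

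**The case against.** **No selection is stated.** A reader might infer that the reported AUC will be the best of many tries and is therefore biased. The text does not support that. It has no rule for picking a winner, and its wording is compatible with reporting every model. Reading the AUC as cross-validated joins two separate sentences. The search for a superior technique in section 13.3 concerns pheno-group clustering. This stands: the bias is conditional on reporting the winner. If all pipelines are reported, or one is named in advance, there is nothing of this kind to correct.

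**The detail may follow.** The promised analysis plan could specify nesting, and the safeguard sentence could mean cross-validating the whole procedure. Both are possible, but neither is written down.

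**The role of the AUC.** It would be wrong to treat it as the headline evidence. Section 13.5 makes tests of individual analytes primary, and the Aim 2c hypothesis is about mechanisms. This stands and limits the weight of the point.

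**The simulations are surrogates.** They omit the Bayesian factor models and the Kaiser rule. If the two-step factor approach is the only one intended, K is 2 and the optimism is about 0.023 (ρ = 0) or 0.016 (ρ = 0.5). This stands: they show size and direction only.

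**An AUC of 0.55 would mislead few readers.** Its 95% interval is about 0.55 ± 1.96 × 0.041, or 0.47 to 0.63. That is fair for the average case. At the 95th percentile of 0.622, however, the lower limit is about 0.54, and no interval is promised in any case.

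**Nesting has its own error.** With stronger signal, 5×5 nesting gave 0.650 against 0.694. That shortfall of 0.044 is larger than the optimism of 0.015 it would replace. This stands, and the choice of outer folds must allow for it.

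**Conclusion.** The point holds as a conditional one. Plain cross-validation does not control the flexibility that section 13.6 describes once a model is chosen among the candidates, and nothing in the section prevents the best AUC from being reported alone. If it is, the expected optimism is about 0.01 to 0.07. That range assumes 3 to 14 pipelines, correlations of 0 to 0.9 and about 100 subjects per group; the simulated biases of 0.015 to 0.061 fall within it. It is largest when true discrimination is weak, and a best-of-six AUC averages about 0.55 under no signal. The documents do not show that the plan will report a biased figure. No sample size or primary test is affected, but the change is cheap and worth making before analysis.

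**What to change.** Amend section 13.6, or settle it in the promised analysis plan, in one of two ways.

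1. Name one pipeline in advance as the reported model, label the others exploratory, and report the cross-validated AUC of every pipeline tried.
2. Use nested cross-validation. Scaling, factor extraction, component retention, tuning and choice of model family are all done within the training folds, and the outer-loop AUC is reported with an interval.

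For the second, use 10 or more outer folds, repeated. The shortfall above came from five outer folds, each training on 80% of the data. Larger training sets should reduce it, although that was not simulated.

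The cost is wording and computing time, and the reported AUC will be lower. The first option avoids the downward error of nesting but gives up choosing the model from the data.

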13.7 Echo Power Calculation and Statistical Analysis

The primary statistical comparison for echo is between group (the HIV+/DD- and HIV+/DD- cohorts) difference in left atrial strain. The sample sizes of 100 subjects in each cohort will provide 80% and 90% power to detect differences of 0.40 and 0.46 standard deviations, respectively. Propensity scores will be the primary tool used to obtain balanced comparisons between cohorts. Three different methods of propensity score adjustment will be applied. The primary analysis method will be based on inverse probability weighting. Secondary approaches will be based on full propensity score matching and doubly-robust estimation. Assessment of distributional overlap and covariate balance will be assessed using the recently developed best practices for propensity score analyses. The primary adjusted analysis of LA strain levels between cohorts will be conducted at that two-sided 0.05 level.

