Hypothesis: The broad representation of biological pathways included on the proteomic and metabolomic panels will enable identification of novel mechanisms underlying DD in HIV+ subjects.

Objective 3: Understand the consequences of diastolic dysfunction.

Aim 3a: To study the effect of DD on mechanics of the left atrium in HIV.

Hypothesis: HIV+/DD+ subjects will have blunted augmentation of left atrial strain during passive leg raise compared to HIV+/DD- and HIV-/DD+ subjects.

Aim 3b: To study the sub-clinical necrosis and myocardial stress in HIV+/DD+ subjects.

Hypothesis: HIV+/DD+ subjects will have higher troponin and NTproBNP levels than HIV+/DD- and HIV-/DD+ subjects.

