5.1 Screening Phase

Subjects who are HIV positive, have been on HAART for ≥ 6 months and are virally suppressed will be screened for participation in the study using the inclusion and exclusion criteria listed below. Eligible patients will be approached to consent to the study. Those who agree to participate will be screened with an echo to determine if they are EF eligible and classified as DD+ or DD-. Diastolic dysfunction criteria are:

- (1) LVEF $> 50\%$
- (2) Evidence of impaired LV relaxation (septal $e' < 7\text{cm/s}$ or lateral $e' < 10\text{cm/s}$)
- (3) Evidence of chronically elevated LV filling pressure or LVH (or concentric remodeling)
 - (a) LA volume index $> 28\text{ml/m}^2$ or

- (b) LV hypertrophy (LV mass index $>95\text{g/m}^2$ in women, $>115\text{g/m}^2$ in men or
- (c) Concentric LV remodeling (relative to wall thickness >0.42)

[figure not shown]

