11.4 Left Atrial Reserve

Left atrial (LA) dysfunction is associated with development of HFpEF. In patients with prevalent HFpEF, LA dysfunction leads to pulmonary hypertension, reduced exercise capacity, and ultimately poor clinical outcomes. This protocol will use novel speckle-tracking image analysis in order to understand subclinical functional abnormalities in the LA. The passive leg raise test will determine the ability of the LA to augment its reservoir and booster function in response to

increased preload. Dynamic changes in LA strain will identify differences between HIV+/DD+, HIV+/DD-, and HIV-/DD+ subjects.

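### Section 13.7 does not test Aim 3a as written: it prints one cohort twice and analyses the level of left atrial strain, not its change with passive leg raise

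*Combined protocol and SAP*

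**What the plan says.** Section 13.7 sets the main echo contrast: "The primary statistical comparison for echo is between group (the HIV+/DD- and HIV+/DD- cohorts) difference in left atrial strain". It then fixes the error rate: "The primary adjusted analysis of LA strain levels between cohorts will be conducted at that two-sided 0.05 level". Inverse probability weighting is the primary adjustment method. The power statement reads: "The sample sizes of 100 subjects in each cohort will provide 80% and 90% power to detect differences of 0.40 and 0.46 standard deviations". The section mentions neither leg raise nor change, and does not name a strain component.

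The hypothesis under Aim 3a (Section 4) is of another kind: "HIV+/DD+ subjects will have blunted augmentation of left atrial strain during passive leg raise compared to HIV+/DD- and HIV-/DD+ subjects". Section 11.4 agrees with the aim. On the purpose of the manoeuvre it says: "The passive leg raise test will determine the ability of the LA to augment its reservoir and booster function". On the measure and the groups it says: "Dynamic changes in LA strain will identify differences between HIV+/DD+, HIV+/DD-, and HIV-/DD+ subjects". Section 7 plans the same dynamic echo protocol for this study and for MESA, the source of the HIV-/DD+ subjects, with one reading center.

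**The concern.** Two things in Section 13.7 do not match the aim it should serve. The cohort pair is wrong on its face. The variable is a level, while the aim concerns a response to increased preload.

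The second mismatch carries the weight. Two cohorts can differ at rest and respond equally, or match at rest and respond differently. If the section is followed as written, a significant result could be reported as support for Aim 3a with no evidence on augmentation, and a null result could be read as refuting it. Rest, leg raise and change also remain open as candidates for the primary variable, so the choice could be made after the data are seen. The HIV-/DD+ half of the aim has no specified echo analysis.

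**Working it through.** **1. The plan's own figure.** Inputs: 100 per cohort, two-sided 0.05, differences of 0.40 and 0.46 SD (Section 13.7), and a two-sample t-test (Section 13.2). By the normal approximation, power = Φ(d·√(n/2) − 1.960), with √(100/2) = 7.071.

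- d = 0.40: 0.40 × 7.071 = 2.828; Φ(0.868) = 80.7%.
- d = 0.46: 0.46 × 7.071 = 3.253; Φ(1.293) = 90.2%.

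The exact noncentral t (198 df) gives 80.4% and 89.9%. The stated figures reproduce.

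**2. The cohort label.** Section 5 plans 100 HIV+/DD+ and 100 HIV+/DD- subjects. Section 13.4 uses the same sentence pattern for fibrosis with the pair printed correctly. With the label corrected the comparison is still 100 versus 100, so step 1 is unchanged.

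**3. Level against change.** Let δ0 be the cohort difference (HIV+/DD+ minus HIV+/DD-) in mean strain at rest, δ1 the difference during leg raise, and δc = δ1 − δ0. Aim 3a says δc < 0. A level analysis tests δ0, or δ1 = δ0 + δc; Section 13.7 does not say which. Take strain with the same SD in both positions.

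- δ0 = −0.40 SD and δc = 0: both levels differ by 0.40 SD, so either level test is significant with probability 80.4%, although nothing is blunted.
- δ0 = 0 and δc < 0: a resting-level test rejects in 5%, whatever the size of δc.
- δ0 > 0 and δc = −δ0: then δ1 = 0, and a leg-raise-level test rejects in 5% although the response is blunted.

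None of these cases depends on the correlation between the two readings.

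**4. Is the change analysed elsewhere in Section 13?** Section 13.2 covers biomarkers, 13.3 phenomapping (where echo data are clustering inputs), 13.4 cMRI, 13.5 proteins and metabolites, and 13.6 integrated molecular models. None specifies a test of augmentation, or an echo comparison with HIV-/DD+ beyond a general remark on power in 13.2.

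**5. What 0.40 SD means for a change.** With equal variances and correlation ρ between rest and leg raise, SD(change) = SD(level) × √(2(1 − ρ)). The documents give no ρ, so the range is an assumption. The exact detectable difference at 80% power is 0.398 SD of the change. In SDs of the level this is:

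| ρ | SD(change)/SD(level) | 0.398 × ratio |
|---|---|---|
| 0.3 | 1.183 | 0.47 |
| 0.5 | 1.000 | 0.40 |
| 0.7 | 0.775 | 0.31 |
| 0.8 | 0.632 | 0.25 |
| 0.9 | 0.447 | 0.18 |

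The power for 0.40 SD of the change stays at 80.4% throughout; only its translation into strain units moves.

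**6. The HIV-/DD+ comparison.** The size of that cohort is not stated. Assuming 200 to 1,000 subjects against 100 HIV+/DD+, power at 0.40 SD is 90.2% to 96.8%, in line with the remark in Section 13.2 that such comparisons have greater power.

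**The case against.** The best defence is that the intent is plain. The duplicated label is a slip. The word for level looks inherited from a template, since Sections 13.2 and 13.4 use it for IL-6 and for fibrosis. Sections 4, 7 and 11.4 all treat the echo measure as dynamic, and Section 13.1 promises a statistical analysis plan before the data are analysed.

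Most of this stands as an account of how the text arose. It does not supply the missing specification. Section 13.7 already fixes a primary comparison, an adjustment method and an error rate, and an analyst following it would analyse a level.

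Three stronger readings are tempting, and the documents do not support them.

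- A reader might infer that the primary echo analysis is null by construction. Nobody could run a cohort against itself, and Sections 5 and 13.4 show which pair is meant.
- A reader might infer that the power statement is wrong, or that analysing the level must lose power. The 0.40 and 0.46 figures are unit-free, and Section 13.2 applies them to any suitably transformed continuous variable. Whether a leg-raise level gives less power than the change depends on ρ and on any resting difference, and the documents give neither. With no resting difference, ρ = 0.5 gives no loss and ρ = 0.3 a gain.
- A reader might infer that a level difference is built in because "LA volume index" helps define DD+. In Section 5.1 it is one of three alternatives under the third criterion, volume is not strain, and the documents do not link it to resting strain.

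**Conclusion.** The point holds. As written, Section 13.7 does not test Aim 3a, and no other part of Section 13 does. The cohort label is a typing error with no numerical consequence. The substantive defect is that the section analyses a level where the aim and Section 11.4 need a change.

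Its size is one of interpretation rather than power: a level test can reject about 80% of the time with no blunting, or only 5% of the time with blunting, depending on the resting difference. Those two figures assume 100 analysable subjects per cohort, an unweighted t-test and, for the first, a 0.40 SD difference in level. The mismatch itself needs no numerical assumption. The design, the sample size and the stated power are unaffected.

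**What to change.** Rewrite Section 13.7 before any echo data are analysed:

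- Primary comparison: HIV+/DD+ versus HIV+/DD- in the change in LA strain, passive leg raise minus rest. Name the strain component, since Section 11.4 mentions both reservoir and booster function.
- Label the 0.40 and 0.46 figures as SDs of that change. The numbers stay.
- Make resting LA strain a secondary variable.
- Add a sensitivity analysis of the change adjusted for resting strain. In groups that were not randomised, the adjusted and unadjusted change can give different answers, so their order should be fixed in advance.
- Add the HIV+/DD+ versus HIV-/DD+ comparison from Aim 3a and state its place in the testing order.

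Do not adjust for LA volume index: it is part of the DD+ definition in Section 5.1, so adjustment would partly remove the contrast under study.

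The cost is protocol and analysis-plan wording and some added analysis. The dynamic echo is already planned with central reading, so no further subjects or measurements are needed.
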